**Table 3-2 Example of imputation** 

Month	Average # of relapses
1	0.20
2	0.19
3	0.18
4	0.17
5	0.16
6	0.15
7	0.14

8	0.13
9	0.11
10	0.11
11	0.11

0.11

12

If a subject discontinues the study on Day 130 (i.e., after 4 months and 10 days) after having one confirmed relapse, his number of relapses from Month 6 on will be imputed from the above table. His total number of relapses will be the sum of 1, 0.15, 0.14, 0.13, 0.11...0.11, which equals to 1.86. Note that the imputed portion of the number of relapses will be the same for subjects who drop out in the same month.

The imputation will only apply to the dropout subjects up to 360 days (i.e., 12 months). After the imputation, the number of days in study for all dropout subjects is 360 days. For those who complete the study, the number of days in study will remain the same as defined in Time in study for aggregate ARR Section 4.1.3.

4) Summary of subject-level ARR without imputation on the full analysis set: For subjects who discontinue the study prematurely, the number of relapses recorded in the study will be used and no imputation will be applied.

#### 4.2.1.4 Missing MS relapse dates

The following obvious corrections will be implemented by programming if the relapse partial start/or end date occurs where only day is missing.

For an incomplete relapse start date where day is missing but month and year are available, the day will be entered as the first day of the month. In case the relapse partial start date is in the same month as the first study drug dose date, the relapse start date will be entered as the first study drug dose date.

For an incomplete relapse end date where day is missing but month and year are available, the day will be entered as the last day of the month. In case the relapse partial end date is in the same month as the last visit date, the relapse end date will be entered as the last visit date. For a relapse is still ongoing at the last visit the relapse end date will be entered as the last visit date.

# 4.2.2 Analyses of secondary variables

Secondary efficacy variables will be analyzed on the full analysis set unless otherwise specified. For most analyses, all three pair-wise treatment comparisons (fingolimod 0.5 mg vs. glatiramer acetate, 0.25 mg vs. glatiramer acetate, and 0.5 mg vs. 0.25 mg) will be provided even though no formal hypothesis will be tested between the 2 fingolimod doses.

#### 4.2.2.1 Magnetic resonance imaging (MRI)

The analyses on MRI parameters will be performed on the full analysis set in the subset of subjects who have MRI scans done during the study. For all MRI data, no visit mapping will be performed for any visit and all analyses will be performed according to the visit recorded in the MRI data set.

The number and volume of Gd + lesion data obtained less than 30 days after use of steroid for treatment of relapses will be excluded from the analysis.

Analyses of MRI variables are summarized in Table 3-3 below and details will be provided in the following section.

Table 3-3 MRI endpoints & analyses

Endpoint	Analysis
Brain atrophy - Percent brain volume change (PBVC) from baseline at Month 12/end of treatment	Rank ANCOVA (treatment, age, baseline normalized brain volume (NBV), and the number of relapses experienced in the previous year before study enrollment) (region will be considered)
	ANCOVA (treatment, age, baseline normalized brain volume, and the number of relapses experienced in the previous year before study enrollment) (region will be considered)
	ANCOVA (treatment, age, baseline Gd + T1 lesion count, and baseline T2 lesion volume (in cc). (region will be considered)
New/newly enlarged T2 lesion count (compared with baseline MRI scan) at Month 12/end of treatment	Negative binomial (treatment, age, baseline T2 lesion count, baseline Gd + T1 lesion count, and the number of relapses experienced in the previous year before study enrollment) (region will be considered)
	Rank ANOVA (treatment, region)
Proportion of subjects free of new/newly- enlarged T2 lesions compared to baseline at Month 12/end of treatment	Logistic regression (treatment, age, baseline T2 lesion count, baseline Gd + T1 lesion count, and the number of relapses experienced in the previous year before study enrollment) (region will be considered)
Change (and % change) from Baseline in T2 lesion volume at Month 12/end of	Rank ANCOVA (treatment, age, baseline T2 lesion volume, and the number of relapses

treatment	experienced in the previous year before study enrollment) (region will be considered)
Gd + T1 lesion count at Month 12/end of treatment	Negative binomial (treatment, age, baseline T2 lesion count, baseline Gd + T1 lesion count, and the number of relapses experienced in the previous year before study enrollment) (region will be considered)
Proportion of subjects free of Gd + T1 lesions at baseline, Month 12/end of treatment	Logistic regression (treatment, age, baseline Gd + T1 lesion count, and the number of relapses experienced in the previous year before study enrollment) (region will be considered)
Gd + T1 lesion volume at Month 12/end of treatment	Rank ANCOVA (treatment, age, baseline Gd + T1 lesion volume, and the number of relapses experienced in the previous year before study enrollment) (region will be considered)
Proportion of subjects free of new T1 lesions compared to baseline at Month 12/end of treatment	Logistic regression (treatment, age, baseline T1 lesion count, baseline Gd + T1 lesion count, and the number of relapses experienced in the previous year before study enrollment) (region will be considered)
Change and % change from baseline in T1 lesion volume at Month 12/end of treatment	Rank ANCOVA (treatment, age, baseline T1 lesion volume, and the number of relapses experienced in the previous year before study enrollment) (region will be considered)
Percent brain volume change (PBVC) from baseline at Month 12/end of treatment	Sensitivity analyses to repeat the same analyses descripted above, but exclude baseline assessments performed > 45 days before randomization and end of treatment
New/newly enlarged T2 lesion count at Month 12/end of study	assessments performed > 45 days after the last dose of study drug.
Gd + T1 lesion count at Month 12/end of treatment	
Proportion of subjects free of new/newly enlarged T2 lesions and proportion of subjects free of Td + T1 lesions at Month 12/end of treatment	
Annualized rate of brain atrophy (ARBA) at Month 12/end of treatment	Sensitivity analyses to adjust for study duration and MRI covariates:  Rank ANCOVA (treatment, age, baseline NBV, baseline Gd + T1 lesion count, and baseline T2

baseline Gd + T1 lesion count, and baseline T2 lesion volume, and the number of relapses experienced in the previous year before study enrollment (region was considered)

[figure not shown]
The number of new or newly enlarging T2 lesions at Month 12/end of treatment and number of Gdenhancing T1 lesions at Month 12/end of treatment will be analyzed using a negative binomial regression model with log link, using treatment as main effect, age, baseline T2 lesion count, baseline Gd-enhancing T1 lesion count, and the number of relapses experienced in the previous year before study enrollment as covariates. An adjustment for region will be considered in the model. For the analysis of T2 lesions, an offset variable will be used in the negative binomial analysis to adjust for the time in years (since start of study drug).

The proportion type variables will be analyzed using a logistic regression model with treatment as main effect, age, corresponding baseline value, baseline Gd-enhancing T1 lesion count, and the number of relapses experienced in the previous year before study enrollment as covariates. An adjustment for country or region will be considered in the model.

The continuous variables (change, percent change, and total volume) will be analyzed using a rank ANCOVA model with treatment as main effect, adjusted for age, corresponding baseline value, and the number of relapses experienced in the previous year before study enrollment as covariates. An adjustment for country or region will be considered. ANCOVA analysis for the percent change in brain volume with the above variables as covariates will be considered as well. In addition, an ANCOVA model with treatment, baseline Gd + T1 lesion count and the T2 volume (in cc) will be performed.

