2.2 Secondary objectives

To evaluate in fingolimod 0.5 mg, fingolimod 0.25 mg, and glatiramer acetate 20 mg groups:

- the change from Baseline in brain volume at Month 12 or end of study
- the number of active T2 lesions (new or newly enlarging lesions compared with Baseline) at Month 12 or end of study.
- the proportion of patients free of new or newly enlarging T2 lesions compared to Baseline at Month 12 or end of study
- the change from Baseline in T2 lesion volume at Month 12 or end of study
- the change from Baseline in the number and volume of T1 hypointense lesions at Month 12 or end of study
- the number and volume of Gd-enhancing T1 lesions at Month 12 or end of study
- the safety and tolerability up to Month 12
- the change from baseline in treatment satisfaction as measured by the Treatment Satisfaction Questionnaire for Medication (TSQM) at Month 12 or end of study

3 Investigational plan

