9.5 Analysis of secondary variables

9.5.1 Efficacy variables

All efficacy analyses of secondary variables specified in this section will be conducted on the full-analysis set unless otherwise specified.

Magnetic resonance imaging (MRI)

The analyses on MRI parameters will be performed on the full analysis set in the subset of patients who have MRI scans done during the study.

The MRI efficacy variables are listed as following:

[figure not shown]
- Percent change in brain volume from baseline at Month 12 or end of study
- Number of new and newly enlarging T2 lesions (compared with baseline MRI scan) at Month 12 or at end of study
- Proportion of patients free of new/newly enlarging T2 lesions compared to baseline at Month 12 or end of study
- Change (and % change) from Baseline in total volume of T2 lesions at Month 12 or end of study
- Number of new T1 hypointense (acute or chronic) lesions compared to baseline, at Month 12 or end of study
- Change and % change from baseline in total volume of T1 hypointense lesions (acute or chronic) at Month 12 or end of study
- Number of Gd-enhancing T1 lesions at Month 12 or end of study
- Total volume of Gd-enhancing T1 lesions at Month 12 or end of study

The number of new or newly enlarging T2 lesions at Month 12 or end of study and number of Gd-enhancing T1 lesions at Month 12 or the end of study will be analyzed using a negative binomial regression model with log link, using treatment, age, baseline T2 lesion number, baseline number of Gd-enhancing T1 lesions, and the number of relapses experienced in the previous year before study enrollment as covariates. An adjustment for country or region can be considered prior to database lock and will be defined in the analysis plan. For the analysis of T2 lesions, an offset variable will be used in the negative binomial analysis to adjust for the time in years (since start of study drug).

The proportion type variables will be analyzed using a logistic regression model with treatment, age, corresponding baseline value, baseline number of Gd-enhancing T1 lesions, and the number of relapses experienced in the previous year before study enrollment as covariates. An adjustment for country or region can be considered prior to database lock and will be defined in the analysis plan.

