## 12.1.1.1 Negative binomial regression model

The primary efficacy variable (aggregate ARR) will be analyzed using a negative binomial regression model. This analysis will be performed on the full analysis set and the per-protocol set. All 3 treatment groups will be used to fit the regression model in the analysis. In addition, the negative binomial regression model will be used for several supportive analyses for aggregate ARR and number of new or newly enlarged T2 lesions.

Negative binomial regression is used for modeling count variables, usually for overdispersed count outcome variables, while adjusting for one or more covariates. In general, Negative binomial regression analyzes the distributed data in the following form

$$Y_i \sim NB(r_i, p_i)$$
, for  $i = 1, \dots, n$ .

where the **negative binomial distribution** is a discrete probability distribution of the number of successes in a sequence of Bernoulli trials before a specified (non-random) number of failures (denoted r) occur with a probability p.

The log of the count variables are modeled as a linear function of the  $X_i$ .

$$\log(y_i) = \beta_0 + \beta_1 x_{1,i} + \dots + \beta_k x_{k,i}$$

Below is an example of the SAS codes used to perform the analysis of the negative binomial regression. The independent variables and covariates in the model may change per analysis defined in this document.

\*\*\*\*\*\*\*\*\*\*\*\*\*\*\*\*\*\*

```
* SAS Codes: Negative binomial regression model
* Variables in the model:
* relnum = number of relapses
* trt = treatment group code
* reg1a = region code
* n2 = number of relapses in previous year
* bledss = baseline EDSS
* sid1a = subject ID
* lnday = log(days in study/365.25)
*********************
proc genmod data=data1;
    class trt regla;
    model relnum=trt reg1a n2 bledss / dist=nb
                                      link=log
                                      offset=lnday maxiter=500 lognb;
    1smeans trt /cl;
    estimate 'A - B' trt 1 - 1 0/\exp;
    estimate 'A - C' trt 1 	 0 	 -1/\exp;
```

```
estimate 'B - C' trt 0 1 -1/exp;

ods output estimates=est;

ods output lsmeans=lst;

run;
```

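### The number of new T1 hypointense lesions is a listed secondary MRI variable, but neither document gives the count an analysis; only a lesion-free proportion and lesion volume are modelled.

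*SAP*

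**What the plan says.** Protocol 2.2 includes among the secondary objectives "the change from Baseline in the number and volume of T1 hypointense lesions at Month 12 or end of study". Protocol 9.5.1 turns this into two separate MRI variables. One is "Number of new T1 hypointense (acute or chronic) lesions compared to baseline, at Month 12 or end of study"; the other is the change and percent change in T1 hypointense volume. Protocol 9.5.1 does not list a T1 lesion-free proportion.

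The negative binomial paragraph in protocol 9.5.1 covers two counts only: one for T2 lesions that are new or have enlarged, and one for Gd-enhancing T1 lesions. SAP 4.2.2.1 repeats that paragraph for the same two counts.

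SAP Table 3-3 gives T1 lesions that are not labelled Gd+ two rows in its main set of analyses. One is "Proportion of subjects free of new T1 lesions compared to baseline at Month 12/end of treatment" (logistic regression). The other is change and percent change in T1 volume (rank ANCOVA). Baseline T1 lesion count appears only as a covariate in the logistic row.

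**The concern.** The protocol names the count as an efficacy variable, and the SAP is where its model should be fixed before unblinding. With no row and no model, the team must either leave the count without a prespecified comparison or choose a model after seeing the data.

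The lesion-free proportion does not fill the gap well. It scores a patient with one new lesion the same as a patient with ten. If treatment mainly reduces how many lesions form, rather than whether any form, the yes/no comparison will often miss an effect that the count would show.

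**Working it through.** **Step 1: set the analyses side by side.** Neither document gives a figure for this endpoint (protocol 9.7, on power for key secondary hypotheses, is marked not applicable), so there is nothing to reproduce. The main check is of the text.

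| Lesion type | Count listed in protocol 9.5.1 | Count model, protocol 9.5.1 | Count row, SAP Table 3-3 | Lesion-free row, SAP Table 3-3 |
|---|---|---|---|---|
| New/newly enlarging T2 | yes | negative binomial | negative binomial | logistic |
| Gd-enhancing T1 | yes | negative binomial | negative binomial | logistic |
| New T1 hypointense | yes | none | none | logistic |

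I read the SAP's plain T1 lesion label as T1 hypointense, because Gd-enhancing T1 lesions are labelled separately throughout.

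**Step 2: check the SAP methods sections.**
- 12.1.1.1 limits the further use of negative binomial regression to "supportive analyses for aggregate ARR and number of new or newly enlarged T2 lesions". This is weak evidence alone, since the Gd+ count is not named there either although 4.2.2.1 assigns it that model.
- 12.1.1.3 has new T1 lesions only as a proportion.
- 12.1.1.5 lists T1 hypointense volume among the MRI variables, but not number.
- 12.1.1.2 refers generically to change from baseline in MRI variables under rank ANCOVA and does not name this count.

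**Step 3: illustrate the loss from dichotomising.**
- From the documents: final arms of 352 (fingolimod 0.5 mg) and 342 (glatiramer), SAP section 10.
- Assumed: 85% with usable scans, borrowed from the 15% dropout assumption in protocol 9.6, so n1 = 0.85 × 352 = 299.2 and n0 = 0.85 × 342 = 290.7.
- Also assumed: rate ratio 0.65, glatiramer mean m0 from 0.2 to 2 new lesions, dispersion k from 1 to 4, two-sided alpha 0.05.

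Formulas, with m1 = 0.65 × m0 and Φ the normal distribution function:
- Count: var(log RR) = (1/m0 + k)/n0 + (1/m1 + k)/n1; power = Φ(|ln 0.65|/SE − 1.96).
- Lesion-free: P = (1 + k·m)^(−1/k) in each arm; var(log OR) = 1/[n0·P0(1−P0)] + 1/[n1·P1(1−P1)]; power = Φ(log OR/SE − 1.96).

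Worked case, m0 = 1 and k = 2:
- Count: var = 3/290.7 + (1/0.65 + 2)/299.2 = 0.0103 + 0.0118 = 0.0221, SE 0.149. Since |ln 0.65| = 0.431, power = Φ(2.90 − 1.96) = 0.83.
- Lesion-free: P0 = 3^(−1/2) = 0.577 and P1 = 2.3^(−1/2) = 0.659. Log OR = 0.349, SE 0.170, power = Φ(2.05 − 1.96) = 0.54.

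The same formulas over the grid:

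| m0 | k | Count | Lesion-free | Loss (points) |
|---|---|---|---|---|
| 0.2 | 1 | 0.49 | 0.43 | 5.5 |
| 0.2 | 2 | 0.44 | 0.37 | 7 |
| 0.3 | 1 | 0.63 | 0.54 | 9 |
| 0.5 | 1 | 0.80 | 0.65 | 14 |
| 0.5 | 4 | 0.53 | 0.34 | 20 |
| 1 | 2 | 0.83 | 0.54 | 29 |
| 2 | 2 | 0.90 | 0.49 | 41 |
| 2 | 4 | 0.68 | 0.29 | 39 |

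Except in the mildest corner (mean 0.2, dispersion 1), the loss lies between about 7 and 41 points. The lesion-free test had lower power in every case run.

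**The case against.** The strongest case on the other side has four parts.

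**The objective is partly met.** It covers number and volume. Volume is analysed, and the occurrence of new lesions is analysed by logistic regression. Volume also captures some of the burden that the proportion ignores. This stands. A reader might infer that the secondary objective goes wholly unanswered; the documents do not support that.

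**The SAP may cover the count indirectly.** SAP section 1 says the data are analysed according to protocol section 9, which still lists the count, and the rank ANCOVA wording for change variables could be stretched to include it. Output tables are listed in RAP Module 7.1, which is not among the documents. So a reader cannot conclude that the count will go unreported; a descriptive table may exist. But protocol 9.5.1 supplies no model to inherit. The rank ANCOVA text in 4.2.2.1 is for continuous variables, and no list names this count. The gap in prespecified analysis remains.

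**Nothing shows a deliberate substitution.** A reader might infer that the SAP swapped the count for a proportion. The gap begins in protocol 9.5.1, which lists the variable without a model. The SAP also adds a lesion-free proportion for Gd+ T1 lesions that protocol 9.5.1 does not list, while keeping the Gd+ count. SAP section 11 shows no text in the available copy, which proves nothing either way. An omission carried forward is the safer reading.

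**The size is assumed.** This stands. With few lesions per patient the two analyses nearly agree; only the direction was the same in every scenario.

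**Conclusion.** The point holds in a limited form. A count that the protocol lists as a secondary MRI efficacy variable has no specified analysis in either document, and the number component of the objective is addressed only through a dichotomised endpoint. The parallel treatment of T2 and Gd+ T1 lesions makes this look like an oversight.

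The illustrated loss of roughly 6 to 41 points of power rests entirely on assumed lesion means, dispersion, effect and scan completeness, and should not be quoted as a property of this trial.

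The consequence is confined to one secondary endpoint. Only the two ARR hypotheses are in the testing hierarchy (SAP 4.2.1.1), no key secondary variable is defined (SAP 4.1.2), and the primary analysis is unaffected. It should be corrected, but it does not threaten the trial's main conclusion.

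**What to change.** Add a row to SAP Table 3-3 and a sentence in 4.2.2.1 for the number of new T1 hypointense lesions versus the baseline scan at Month 12/end of treatment. Specify:
- negative binomial regression with log link;
- treatment, age, baseline T1 hypointense lesion count, baseline Gd+ T1 count and relapses in the previous year, with region considered. These are the covariates of the existing logistic row for new T1 lesions;
- the offset already used for the T2 count, time in years since start of study drug.

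Keep the proportion free of new T1 lesions as supportive, and name the count in 12.1.1.1 so that the sections agree.

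Negative binomial is the natural choice because the other two lesion counts use it, but the protocol does not require it. If the sponsor decides against modelling the count, SAP section 11 should say so and give the reason.

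The cost is one extra model on the new-lesion readings that the lesion-free proportion already needs, plus one more MRI endpoint compared without multiplicity control.

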#### 4.2.2.2 Relapses

All relapse-related analyses use confirmed relapses only, unless otherwise specified.

Novartis Confidential Page 36

[figure not shown]
RAP Module 3 Protocol No. CFTY720D2312

## 4.2.2.5 EDSS Scores

Summary statistics will be presented on the FAS for the observed EDSS scores by visit and treatment. The change from baseline to end of study in EDSS score will be summarized on the FAS as well.

Novartis Confidential Page 39

RAP Module 3 Protocol No. CFTY720D2312

Novartis

## 7 Health-related Quality of Life (QoL)

## **7.3 TSQM** (Version 1.4)

Treatment Satisfaction Questionnaire for Medication (TSQM) was developed and validated as a general measure for treatment satisfaction. The TSQM version 1.4 modified will be used, which contains 14 items assessing the following 4 domains: Global Satisfaction, Effectiveness, Side Effects, and Convenience. This patient reported outcome (PRO) must be completed prior to any other study visit assessments at the specified visits according to Table 6-1 assessment schedule in study protocol.

Scores for the TSQM version 1.4 will be generated using the authors' scoring algorithm. Missing data will be treated in accordance with the authors' guidelines (Atkinson et al 2004) as follows:

#### **EFFECTIVENESS:**

```
Score = \{[(sum of items 1-3) - 3] / 18\} * 100
```

If only one item is missing, Score =  $\{[(sum of available items in 1-3) - 2] / 12\} * 100$ 

#### SIDE EFFECTS:

If Question 4 is answered "No" then Score = 100.

#### Otherwise:

Score = 
$$\{[(sum of items 5-8) - 4] / 16\} * 100$$

If only one item is missing, Score =  $\{[(sum of available items in 5-8) - 3] / 12\} * 100$ 

Protocol No. CFTY720D2312

#### **CONVENIENCE:**

Score =  $\{[(sum of items 9-11) - 3] / 18\} * 100$ 

If only one item is missing, Score =  $\{[(sum of available items in 9-11) - 2] / 12\} * 100$ 

#### GLOBAL SATISFACTION:

Score =  $\{[(sum of items 12-14) - 3] / 14\} * 100$ 

If only one item is missing:

Item 12 or 13 missing: Score =  $\{[(\text{sum of available items in } 12-14) - 2] / 10\} * 100$ 

Item 14 missing: Score =  $\{[(sum of available items in 12-14) - 2] / 8\} * 100$ 

The higher summary scores indicate better satisfaction with study drug.

Scores for each scale at scheduled visits will be summarized by treatment group with n, mean SD, minimum, Q1, median, Q3, and maximum. The change from baseline score will be compared within treatment group by Wilcoxon signed-rank test (also known simply as the Wilcoxon sign test).

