6.6.1.1 Treatment Satisfaction Questionnaire for Medication v1.4 (TSQM v1.4)

Treatment Satisfaction Questionnaire for Medication (TSQM) was developed and validated as a general measure for treatment satisfaction (Atkinson 2004). The TSQM version 1.4 contains 14 items assessing the following 4 domains: Global Satisfaction, Effectiveness, Side Effects, and Convenience. This PRO must be completed prior to any other study visits assessments at the baseline, 6 and 12 month visits.

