9.5.4 Health related quality of life

Analysis of Treatment Satisfaction Questionnaire for Medication (TSQM v1.4)

The primary analysis for the TSQM will be between group change in Global Satisfaction from baseline to Month 12. Analyses of the Effectiveness, Side Effects, and Convenience domains will also be conducted.

For the TSQM, responses to items are summed and transformed so that higher scores indicate greater satisfaction. Specifically, TSQM scale scores are computed by adding the items loading on each domain. The lowest possible score is subtracted from the composite score and divided by the greatest possible score range. This provides a transformed score between 0 and 1 that is then multiplied by 100. If more than one item is missing from a subscale of the TSQM for a particular patient, this subscale should be considered invalid for that respondent.

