# 1 Statistical methods planned in the protocol and determination of sample size

Data will be analyzed by statisticians and statistical programmers assigned to this study according to the data analysis section 9 of the study protocol and protocol amendments which is available in Appendix 16.1.1 of the CSR. Important information is given in the following sections and details are provided, as applicable, in Appendix 16.1.9 of the CSR.

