## 12.1.1.6 Analysis of Covariance (ANCOVA) for quality of life (QoL) variables

## One sample t-test for quality of life (QoL) variables

The regular one-sample t-test will be used to perform within-group comparisons of continuous (or quantitative) efficacy variables where the normality assumption is held reasonably well. The within-

run;

group analyses for continuous / quantitative variables will compare assessments for the end of treatment vs. baseline within each treatment group. Examples of such analysis include the within group comparisons of the quality of life variable: change from baseline in TSQM total score.

Below is an example of the SAS codes used to perform the analysis. All 3 treatment groups will be used in the model.

```
*************
* * SAS Codes: One sample t-test
* V1 = First timepoint --- e.g.: (baseline);
* V2 = Second timepoint --- e.g.: (post-baseline visit, end of treatment);
* PID = Subject ID or number of observations;
* diff= difference between two timepoints (higher scores indicate better
results);
* NOTE: First, prepare and extract the data for each treatment group.
* Then, in each treatment group, break up the data into the 2 timepoints.
st Ensure that each subject has a value at both timepoints (V1 and V2).
****************
data one;
  input PID V1 V2;
  diff = V2 - V1;
proc ttest data = one sides=u;
  by treat;
  var = diff;
```

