## 12.1.1.7 Wilcoxon sign test for quality of life (QoL) variables

Wilcoxon signed-rank test (also known simply as the Wilcoxon sign test) can be thought of as the non-parametric equivalent of the regular one-sample t-test. It will be used to perform all within-group comparisons of continuous (or quantitative) efficacy variables. The within-group analyses for continuous / quantitative variables will compare assessments for the end of treatment vs. baseline within each treatment group. Examples of such analysis include the within group comparisons of the quality of life variable: change from baseline in TSQM total score.

Below is an example of the SAS codes used to perform the analysis. All 3 treatment groups will be used in the model.

\*\*\*\*\*\*\*\*\*\*\*\*\*

```
* * SAS Codes: Wilcoxon signed-rank test (or Wilcoxon sign test)
* V1 = First timepoint --- e.g.: (baseline);
* V2 = Second timepoint --- e.g.: (post-baseline visit, end of treatment);
* PID = Subject ID or number of observations;
* diff= difference between two timepoints;
* NOTE: First, prepare and extract the data for each treatment group.
* Then, in each treatment group, break up the data into the 2 timepoints.
* Ensure that each subject has a value at both timepoints (V1 and V2).
**************************
data one;
  input PID V1 V2;
  diff = V2 - V1;
proc univariate data = one;
  by treat;
  var = diff;
run;
```

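### SAP 7.3 states only a within-arm Wilcoxon test for the TSQM and neither states nor points to the between-arm comparison that protocol 9.5.4 makes the primary TSQM analysis

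*SAP*

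**What the plan says.** Protocol 2.2 lists change from baseline in TSQM among the secondary objectives, to be evaluated in all three arms. Protocol 9.5.4 then says what the main analysis is: "The primary analysis for the TSQM will be between group change in Global Satisfaction from baseline to Month 12". It adds that the Effectiveness, Side Effects and Convenience domains will be analysed as well. It names no test, model or covariates.

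SAP 7.3 gives the scoring of the four domains, the rules for a missing item, descriptive statistics by arm, and one inferential statement: "The change from baseline score will be compared within treatment group by Wilcoxon signed-rank test". It does not name Global Satisfaction as the main domain, does not single out Month 12, and contains no comparison between arms and no pointer to one.

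The methods appendix has two QoL entries. SAP 12.1.1.6 is headed "Analysis of Covariance (ANCOVA) for quality of life (QoL) variables", but the text and code visible under that heading are a within-group one-sample t-test. SAP 12.1.1.7 describes the Wilcoxon signed-rank test: "It will be used to perform all within-group comparisons of continuous (or quantitative) efficacy variables". Both give TSQM change from baseline as their example.

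**The concern.** The two documents ask different questions. The protocol asks whether satisfaction changes more in one randomised arm than in another. The rule in SAP 7.3 asks, arm by arm, whether the change differs from zero. Three answers to the second question do not give an estimate, a confidence interval or a test for the first.

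The distinction matters for this instrument. The TSQM rates a medication, and its baseline is taken before study drug: "This PRO must be completed prior to any other study visits assessments at the baseline, 6 and 12 month visits". Under protocol 4.2, patients on dimethyl fumarate, glatiramer acetate or interferon beta may continue until the day before Day 1. A change from baseline can therefore reflect the earlier drug as well as the study drug. Randomisation balances that across arms in expectation, but only a between-arm comparison makes use of the balance.

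A reader given only within-arm p-values is likely to compare them. That can suggest a difference that is not there, or hide one that is.

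**Working it through.** **Reading check.** No sample size or power is stated for the TSQM, so there is no planned figure to reproduce. The check is whether visible SAP text supplies the protocol's analysis.

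- *SAP 7.3:* within-arm test only. Its closing paragraph reads as complete.
- *SAP 12.1.1.6 and 12.1.1.7, visible text:* within-group only.
- *SAP 1:* data are analysed "according to the data analysis section 9 of the study protocol and protocol amendments". This points back to protocol 9.5.4, which gives no model, covariates or contrasts.
- *SAP 2:* between-treatment contrasts go into the output, and tables show each fingolimod dose against glatiramer acetate. The example is the relapse rate; the TSQM is not named.
- *SAP 4.2.2:* "For most analyses, all three pair-wise treatment comparisons" will be provided. The wording covers most analyses, and 7.3 does not refer to it.
- *SAP 12.1.1:* ANCOVA uses data from all three arms. The TSQM is not named.

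So the analysis may be intended, but no visible sentence applies a between-arm model to the TSQM.

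**Size, as an illustration.** The documents give no TSQM effect, SD or completion rate. Assumptions: normally distributed change scores; Month 12 data in 85% of patients (borrowed from the 15% drop-out in SAP 10), varied from 70% to 100%; final arm sizes from SAP 10 of 352 (0.5 mg) and 342 (glatiramer acetate).

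At 85%: 0.85 × 352 = 299 and 0.85 × 342 = 291. At 70%: 246 and 239.

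*Equal true change in both arms.* Let p1 and p0 be the power of a two-sided 5% one-sample t-test for a change of d SD (noncentral t, noncentrality d√n). The chance that exactly one arm is significant is p1(1 − p0) + p0(1 − p1). For d = 0.10 at 85%: p1 = 0.407 and p0 = 0.398, giving 0.407 × 0.602 + 0.398 × 0.593 = 0.48.

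| True change in both arms (SD) | Exactly one arm significant, 85% | Range, 70–100% completion |
|---|---|---|
| 0.05 | 24% | 21–26% |
| 0.10 | 48% | 45–50% |
| 0.15 | 40% | 33–46% |
| 0.20 | 13% | 8–22% |
| 0.25 | 2% | 0.7–5% |
| 0.30 | 0.2% | 0.03–0.7% |

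A simulation of 2,000 trials using the signed-rank test itself, with 299 and 291 patients, gave 23, 47, 40, 15, 3 and 0.2%. Figures for 0.25 mg and glatiramer acetate are almost the same (24, 48, 39, 12, 2 and 0.1%).

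*Unequal true change, 0.4 SD on 0.5 mg and 0.2 SD on glatiramer acetate.* Within-arm power is about 1.00 and 0.925, so both arms are significant in 1.00 × 0.925 = 93% of trials (87–96% over the completion range). The within-arm results then usually show no contrast. For the same 0.2 SD difference, a two-sample t-test has noncentrality 0.2/√(1/299 + 1/291) = 2.43 and power 68% (59–75%). The 95% CI half-width is 1.96 × √(1/299 + 1/291) = 0.16 SD.

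**The case against.** The strongest reply is that the SAP should be read as a whole. Section 1 binds the analysis to protocol section 9. Section 2 says which contrasts are displayed. Section 12.1.1 says ANCOVA uses all arms, and 12.1.1.6 is headed as an ANCOVA for QoL variables. Section 4.2.2 promises pairwise comparisons for most secondary variables, and since 12.1.1.7 gives TSQM change as an example of an efficacy variable, that promise arguably reaches the TSQM. Parts of section 7 and probably of 12.1.1.6 are blacked out, and text lost in that way is not missing from the plan.

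Much of this stands. A reader might infer that the SAP contains no between-arm TSQM analysis, or that the sponsor dropped the protocol's analysis. The documents do not support either reading: method, arms and contrasts are all hinted at in general text, and a model may lie under the blacked-out part.

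It does not remove the conflict in 7.3. None of the general statements names the TSQM in a between-arm analysis, the protocol text they lead back to has no model, and every visible sentence that does name a TSQM test is within-group.

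It is also fair to say that the SAP sets no rule for comparing within-arm p-values, and that the risk of a false contrast is confined to small true changes.

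**Conclusion.** The TSQM rule in SAP 7.3 is wrong as written: followed literally, it does not deliver the analysis that protocol 9.5.4 calls primary for this instrument. The finding is limited to what 7.3 states and to its missing cross-reference.

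The consequence is moderate. The TSQM is a secondary objective outside the two-step test of the relapse rate, so the type I error and power of the primary tests are unaffected. What is at stake is whether the reported TSQM result can be read as a comparison of treatments. Under the assumptions above, within-arm tests would show a contrast where none exists in 13–48% of trials for equal true changes of 0.05–0.20 SD at 85% completion, and in 2% or fewer from 0.25 SD upwards. They would usually mask a difference when both changes are larger. These percentages rest on assumed effects and completion. The mismatch between the two documents does not.

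**What to change.** In SAP 7.3, state a two-sided between-arm comparison of the change in Global Satisfaction from baseline to Month 12, for each fingolimod dose against glatiramer acetate, with an estimate and 95% CI. Then apply the same comparison to the other three domains. One option is an ANCOVA on all three arms with treatment, baseline score and region. The protocol names no covariates, so these should be marked as the SAP's choice. If such a model already exists in 12.1.1.6, a cross-reference from 7.3 is enough. Keep the within-arm tests and label them descriptive.

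The cost is a few sentences of SAP text and one model per domain on data already collected. It adds no endpoint and does not touch the primary testing procedure.
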